5.2 Technical Approach

6. Observed items and testing time points

6.1 Intake

Daily intake and time of intake were recorded during the perioperative period, and patients were followed up at 1 month postoperatively, 3 months postoperatively, and 6 months postoperatively for intake and time of intake.

6.2 Nutrition indicators

Serum albumin (ALB), prealbumin (PA), total serum protein (TP), and transferrin were collected from subjects on day 1 of admission, day 6 postoperatively, 1 month postoperatively, 3 months postoperatively, and 6 months postoperatively.

6.3 Liver function indicators

The patients' alanine aminotransferase (ALT), alanine transaminase (AST), γ -glutamyl transferase (GGT), cholinesterase (CHE), and total bilirubin (TBIL) were collected on the 1st day of the patients'

admission, on the 6th day of the postoperative period, at 1 month postoperatively, at 3 months postoperatively, and at 6 months postoperatively.

6.4 Medical costs

After the patients were discharged from the hospital, the patients' postoperative length of stay, total hospitalization costs, and drug costs were recorded;

6.5 Clinical outcomes

The time of occurrence of postoperative complications and symptoms of the subjects were recorded daily during the patients' hospitalization, and the recurrence-free survival and quality of survival were followed up at 1 month, 3 months, and 6 months postoperatively.

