	
his/her supplementation must be completed before 1h before bedtime.
 
2. Biological sample collection:
 
The remaining post-test serum samples need to be collected for metabolomics analysis from patients on day 1 of admission, postoperative day 6, postoperative 1 month, postoperative 3 months, and postoperative 6 months.
 
3. Clinical data collection:
 
1) General information: gender, age, height, weight, BMI, ICG 15min retention time, name of surgery, duration of surgery, blood loss, blood transfusion, tumor stage, NRS2002, GLIM malnutrition assessment (diagnostic) criteria diagnosis.
 
2) Nutritional indicators: Nutritional indicators such as serum albumin (ALB), prealbumin (PA), transferrin (TRF), and total serum protein (TP) were collected from patients on the 1st day of admission, the 6th postoperative day, 1 month postoperatively, 3 months postoperatively, and 6 months postoperatively.
 
(3) Liver function indexes: Liver function indexes such as alanine aminotransferase(ALT), alanine transaminase(AST), γ-glutamyltransferase (GGT), cholinesterase (CHE), and total bilirubin (TBIL) were collected on the 1st day of admission, the 6th postoperative day, 1 month postoperatively, 3 months postoperatively, and 6 months postoperatively.
 
(4) Clinical outcome: collect the patients' postoperative clinical outcome indicators, such as: postoperative complication rate, recurrence-free survival, and quality of survival.
 
(5) Medical costs: collect the total cost of the patients' hospitalization, the cost of anti-infective drugs, and the cost of albumin during hospitalization.

Evaluation of the	
Indicators of effectiveness evaluation
 
Main efficacy indicators: serum albumin (ALB)
 
Secondary efficacy indicators: serum prealbumin (PA), alanine

efficacy of treatment	aminotransferase (ALT), azelaic transaminase (AST), cholinesterase (CHE), total bilirubin (TBIL), total hospitalization costs, relapse-free survival, and quality of life
	
Safety evaluation indicators
 
Incidence of gastrointestinal symptoms such as abdominal distension, diarrhea, nausea and vomiting, incidence of postoperative complications, and length of postoperative hospitalization

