7.2 Clinical outcomes

1) Post-operative complications

a) Postoperative infections: surgical site infections (SSI), remote infections (RI) and bacteremia.

SSI: Shallow/deep incision SSI and organ/space SSI were defined as redness, swelling, heat, pain, and purulent discharge observed in any incision or space operated on intraoperatively, or the need for a new drain within 30 days postoperatively.

Distant infections: including cholangitis, enteritis, pneumonia, catheter-related infections, and urinary tract infections, defined as fever greater than 38.5°C, leukocytosis, and bacteria detected in

sputum, catheter tips, and urine and feces.

Bacteremia: Bacteremia is diagnosed when a strain is cultured from a single blood culture. And when the strain is identified as coagulase-negative staphylococci, it is considered contaminating; coagulase-negative staphylococci may be considered the causative agent when isolated from two or more blood cultures.

b) Bile leakage

Fluid with a bilirubin concentration of at least three times the serum bilirubin concentration drained through an abdominal drain on or after postoperative day 3. Regardless of the initial bilirubin concentration of the drain placed through surgery, the need for radiologic (i.e., interventional drainage) or surgical intervention (i.e., relative to cesarean section) for biliary collection or biliary peritonitis is also part of the diagnosis of bile leakage.

c) Liver failure after hepatectomy

Elevated serum bilirubin concentration and elevated INR on or after postoperative day 5 compared to the previous day; or coagulation factors such as fresh frozen plasma (FFP) are required to maintain normal INR values on or after postoperative day 5 in combination with hyperbilirubinemia.

- 2) Total hospitalization cost: the total cost of the patient from admission to discharge;
- 3) Recurrence-free survival: the time from the start of the patient's hepatectomy to the first detection of tumor recurrence;
- 4) Quality of Survival: Quality of Survival was evaluated by the EORTC QLQ - HCC18 scale (Appendix 1);
- 5) Safety, diarrhea, vomiting: complaints of gastrointestinal distress that occur after the patient has initiated nutritional support therapy, with diarrhea defined as unformed stools more than three times per day.

8. Adverse Events Watch

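### Complications are scheduled for recording only until discharge, with no common window, so later events may be undercounted and, if stays differ, the comparison could favour the group discharged earlier

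*Combined protocol and SAP*

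**What the plan says.** - **Recording schedule (6.5 Clinical outcomes).** "The time of occurrence of postoperative complications and symptoms of the subjects were recorded daily during the" hospital stay. The same sentence continues with what is collected later: "the recurrence-free survival and quality of survival were followed up at 1 month, 3 months, and 6 months postoperatively". Complications are not in that second list.
- **Definitions (7.2 Clinical outcomes).** One criterion for surgical-site infection is "the need for a new drain within 30 days postoperatively". Bile leakage is judged on fluid "drained through an abdominal drain on or after postoperative day 3", and liver failure on "Elevated serum bilirubin concentration and elevated INR on or after postoperative day 5 compared to the previous day". Both of these have a first day and no last day.
- **Adverse events (section 8).** Events reported or observed between enrolment and study end, or early withdrawal, must be documented. An adverse event is defined as one that follows receipt of the snack.
- **Analysis (3.2 Data analysis, 5.1 item 5, section 10).** Count data, including the complication rate, are compared by chi-square test. No time window and no allowance for observation time are given.
- **Role of the outcome.** The synopsis lists as safety indicators "incidence of postoperative complications, and length of postoperative hospitalization". Section 2.1 names the complication rate in the primary purpose. The primary efficacy indicator is serum albumin.

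**The concern.** If 6.5 is followed as written, each patient's observation period for complications is that patient's hospital stay. A surgical-site infection or bile leak that appears at home has no scheduled place in the endpoint data. At least the new-drain criterion cannot then be assessed to day 30 in anyone discharged sooner.

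Stay is also compared between the groups, and treatment is open and chosen by the patient, so nothing ensures equal stays. A group that goes home sooner has less time in which events can be recorded. A crude comparison of proportions would read that as fewer complications. The complication rate is part of the stated purpose, so a reader will take a lower rate in the snack group as evidence of benefit.

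**Working it through.** **1. The plan's own figure.** The plan states no complication rate, event count or power. Its only calculation is the albumin sample size. With a difference of 37.5 − 34.2 = 3.3 g/L and SD √((3.9² + 5.4²)/2) = 4.71, two-sided α of 0.05 and 90% power, the noncentral t calculation gives 44 per group (power 0.901). That matches the plan but does not bear on complications, so everything below is illustration.

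**2. Inputs, all assumed.** The true 30-day risk is the same in both groups. Onset is exponential with parameter m, truncated at day 30. Everyone in a group is discharged on one day, and nothing is recorded after it. The share of 30-day events recorded by discharge day x is

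F(x) = (1 − e^(−x/m)) / (1 − e^(−30/m)).

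With equal true risks, the recorded-rate ratio is F(shorter stay)/F(longer stay).

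**3. Stays of 7 against 9 days.**

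| m (days) | F(7) | F(9) | Ratio |
|---|---|---|---|
| 6 | 0.6886/0.9933 = 0.693 | 0.7769/0.9933 = 0.782 | 0.886 |
| 8 | 0.5831/0.9765 = 0.597 | 0.6753/0.9765 = 0.692 | 0.863 |
| 14 | 0.3935/0.8827 = 0.446 | 0.4742/0.8827 = 0.537 | 0.830 |

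The apparent relative reduction is 11% to 17% with no true difference. The unrecorded share runs from 1 − 0.782 = 22% to 1 − 0.446 = 55%. Here m is the parameter before truncation. After truncation, the mean onset is 5.8 days for m = 6 and 10.0 days for m = 14.

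**4. Equal stays.** For any x, F(x)/F(x) = 1.00. There is no bias in the ratio, only undercounting. At day 9 in both groups, using the values above, 22% (m = 6) to 46% (m = 14) of events are missed.

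**5. A wider grid.** True risk was set at 20% to 40%, median onset at day 5, 8 or 15 (the last taken as uniform over 30 days), and discharge at day 8 against 9, 8 against 10, or 7 against 10.

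- The recorded-rate ratio ranges from 0.70 to 0.94, and the spurious difference from 0.7 to 5.3 percentage points.
- Example: with 30% risk and median onset at day 8, the onset rate solves to 0.0736 per day, so F(8) = 0.500 and F(10) = 0.585. Recorded rates are 15.0% and 17.6%, a ratio of 0.85.
- At 53 per group, the chance of a significant result in the false direction is about 3% to 10%. The main harm is a biased estimate and missed events, not a false positive test.
- With discharge at day 9 in both groups, 28% to 70% of events are missed over this onset range.

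**6. Section 8 beside 6.5 and 7.2.** Section 8 reaches past discharge, but its definition depends on the snack, which controls do not receive, and nothing says that its records enter the 7.2 rate. If they were used in practice, later events might be collected more fully in the snack group, which would push the comparison the other way.

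**The case against.** The strongest reply is that the plan does look beyond discharge. Section 8 asks for adverse events to study end with onset times and counts an event needing hospitalization as serious. Readmission for an infection or bile leak would then be documented, at least in the snack group. Section 9 repeats that all adverse events are recorded, and neither 3.2 nor 5.1 cuts the complication rate off at discharge. This stands to the extent that a reader may not infer that later events are never captured. It does not close the gap, because the route into the endpoint is unstated and the definition does not clearly cover controls.

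Three further points also stand.

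- The phrase "or the need for a new drain within 30 days postoperatively" may qualify only the drain criterion. A reader might infer that the plan defines a 30-day complication rate that its data cannot supply, but no such rate is defined anywhere.
- A reader might infer that the group discharged earlier will show fewer complications. That needs both different stays and events after discharge, and the documents give figures for neither. Complications also prolong stay, so a shorter stay may partly reflect a real benefit. Inpatient data alone cannot separate the two.
- The illustration gives each group a single discharge day and applies one onset curve to components with different time criteria. Its size is indicative only.

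**Conclusion.** The point holds in conditional form. The complication endpoint has a scheduled recording period that ends at discharge, definitions that reach or may reach beyond it, no common window, and a crude comparison. Undercounting is possible in both groups. Bias towards the group discharged earlier is possible if stays differ.

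Its size cannot be taken from the documents. Under the 7 against 9 day assumption the recorded-rate ratio is about 0.83 to 0.89, and with equal stays it is 1.00. The documents support neither a definite bias nor a total loss of post-discharge events.

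Albumin is unaffected. This is a change that should be made because it is cheap and the complication rate is part of the stated purpose. It does not threaten the primary analysis.

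**What to change.** - **6.5:** Record every complication defined in 7.2 up to postoperative day 30 in both groups, whatever the discharge date. Use the existing 1-month follow-up to ask about post-discharge events and to check records for them. If that contact falls before day 30, complete the remaining days from records.
- **3.2, 5.1 and section 10:** Name the fixed 30-day rate as the quantity compared between groups.
- **Section 8:** State that its records feed the complication endpoint identically in both arms, including controls, who receive no snack.

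The cost is one extra item at a visit that is already scheduled and a somewhat higher recorded complication rate. The change concerns outcome recording only and alters no treatment.

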Statistical methods	
Descriptive statistics were performed on the clinical data, and measures that conformed to normal distribution were expressed as mean±standard deviation ($\bar{x} \pm s$), and t-test was used between groups, and measures that did not conform to normal distribution were expressed as median (interquartile spacing) [M(IQR)], and Mann-Whitney U test was used between groups. Count data were expressed as percentages [n(%)], and the chi-square test was used for between-group comparisons, with $P<0.05$ considered statistically significant. The Kaplan-Meier method in STATA 12.0 was used to calculate the recurrence rate and recurrence-free survival in each group, and the log-rank test was used for intergroup comparison.

Duration of the study	24 months

catalogs

1. Research background	1
2. Research purpose	4
3. Types of Research Designs and Experimental Steps	4
4. Case selection	9
5. Research Methodology and Technical Approach.....	10
6. Observed items and testing time points	12
7. Criteria for evaluating the efficacy of treatment	13
8. Adverse Events Watch.....	14
9. Data security monitoring.....	16
10. Statistical processing	16
11. Ethical principles of clinical research.....	17
12. Reference	17

1. Research background

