2.1 Primary purpose

To observe the effects of late-evening snacks on the nutritional status, liver function recovery, complication rate and long-term prognosis of hepatocellular carcinoma patients who underwent hepatectomy, and to further explore the effects of late-evening snacks on the metabolic pattern of the patients through metabolomics, and to identify the serum differential metabolites, in order to initially investigate the potential mechanism of late-evening snacks to improve the nutritional status of the patients, and to provide theoretical basis for the development of an effective nutritional regimen in the clinic.

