3.1 Types of Research Designs

Types of study designs: single-center, prospective cohort studies

Research Center: Drum Tower Hospital, Medical School of Nanjing University

Grouping method: non-randomized, open, enrolled according to patients' wishes

[figure not shown]
Sample size calculation basis and formula:

This study was a single-center prospective cohort study with two groups, the test group and the control group, and the serum albumin level of the study subjects was the primary endpoint outcome indicator observed. Based on the review of previous literature^[28] and reference to the results of the pretest, it was expected that the albumin level before LES intervention was 34.2 ± 3.9 g/L and the albumin level

after LES intervention was 37.5 ± 5.4 g/L, with a two-sided $\alpha=0.05$ and a degree of certainty of $1-\beta=90\%$. Using PASS15 software can be calculated to obtain $n=88$ cases. Based on the 1:1 grouping, 44 subjects were needed in each of the test and control groups, and assuming a 20% subject dropout rate, the final minimum number of subjects needed was 53 in each of the test and control groups, for a total of at least 106 subjects included.

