3.2 Experimental Steps

The specific steps of the study are as follows:

Pre-procedure preparation:

According to the literature research, establish the form of patients' clinicopathological data that need to be collected, including basic information (age, gender, hospitalization number), pre-surgical laboratory examination (nutritional indexes, liver function, renal function, coagulation function, blood routine, tumor markers such as alpha-fetoprotein, etc.), surgical records (tumor location, size, number, intra-operative bleeding, etc.), post-surgical laboratory examination, tumor recurrence and treatment modality and patient survival, etc., as well as the establishment of a dietary matching table, respectively writing the dietary education content of the experimental group and the control group, in order to personalize the guidance of the patient's postoperative diet and the correct understanding of the importance of dietary therapy. A case questionnaire was set up for the enrolled patients, and the relevant data of the enrolled patients were recorded in the form.

Screening and Trial:

Patients who were admitted to the Department of Hepatobiliary Pancreatic Surgery of Drum Tower Hospital affiliated to Nanjing University School of Medicine, from February 2024 to January 2025 and met the enrollment criteria were selected for inclusion in this study. The grouping was not randomized and blinded, and all patients were enrolled according to their individual wishes and divided into a test group (53 cases) and a control group (53 cases). The purpose of the study, the content of the investigation, the principle of confidentiality were explained to the patients or their families at the time of their admission to the hospital to reduce the concerns of the respondents, and the subjects were included in the study after signing the informed consent form with their consent.

1. Treatment program:

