A data safety monitoring program will be established for clinical studies according to the level of risk. All adverse events will be recorded in detail, appropriately handled and followed up until properly resolved or stabilized, and serious adverse events and unintended events, etc., will be reported to the Ethics Committee, the competent authority, the sponsor, and the drug regulatory authority in a timely manner according to the regulations; the principal investigator will conduct a cumulative review of all adverse events on a regular basis, and convene a meeting of the investigators to assess the risks and benefits of the study, if necessary; the injuries or discomfort is no more likely and no greater in magnitude than that encountered in daily life or than that of a routine examination, and that data and safety monitoring can be accomplished by the principal investigator.

10. Statistical processing

应用 SPSS26.0 统计软件对临床数据进行描述性统计，符合正态分布的计量资料以均数±标

准差($\bar{x} \pm s$)表示, 组间采用 t 检验, 不符合正态分布的计量资料以中位数(四分位间距) [M(IQR)] 表示, 组间采用 Mann-Whitney U 检验。计数资料用百分比[n(%)]表示, 组间比较采用卡方检验, $P<0.05$ 为有显著性统计学意义。采用 STATA12.0 中的 Kaplan-Meier 法计算各组复发率及无复发生存期, log-rank 检验进行组间比较。SPSS26.0 statistical software was applied to carry out descriptive statistics of the clinical data, and the measurements that conformed to normal distribution were expressed as mean \pm standard deviation ($\bar{x} \pm s$), and t-test was used between the groups, and the measurements that did not conform to normal distribution were expressed as median (inter-quartile spacing) [M(IQR)], and Mann-Whitney U-test was used between the groups. Count data were expressed as percentages [n(%)], and the chi-square test was used for between-group comparisons, with $P<0.05$ considered statistically significant. The Kaplan-Meier method in STATA 12.0 was used to calculate the recurrence rate and recurrence-free survival in each group, and the log-rank test was used for between-group comparisons.

11. Ethical principles of clinical research

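### Long-term prognosis is a stated purpose, but recurrence follow-up is scheduled only to 6 months after surgery and no cut-off date is given

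*Combined protocol and SAP*

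**What the plan says.** - **Purpose.** Section 2.1, headed as the primary purpose, covers the effect of late-evening snacks on "complication rate and long-term prognosis of hepatocellular carcinoma patients who underwent hepatectomy". The synopsis has the same words under research purpose.
- **Endpoint.** The synopsis lists recurrence-free survival (RFS) among the secondary indicators; overall survival is not listed. Section 7.2(3) defines RFS as "the time from the start of the patient's hepatectomy to the first detection of tumor recurrence". It gives no horizon, cut-off or censoring rule, and death is not counted.
- **Follow-up.** Section 6.5 states that "the recurrence-free survival and quality of survival were followed up at 1 month, 3 months, and 6 months postoperatively". Intake, laboratory tests and metabolomics (6.1 to 6.3 and 6.6) also end at 6 months.
- **Data form.** Section 3.2 includes "tumor recurrence and treatment modality and patient survival" among the items to record, without a time point.
- **Analysis.** Section 10: "The Kaplan-Meier method in STATA 12.0 was used to calculate the recurrence rate and recurrence-free survival in each group", with a log-rank comparison between groups.
- **Calendar.** Section 3.2 includes patients admitted "from February 2024 to January 2025 and met the enrollment criteria were selected for inclusion in this study". The synopsis gives "Duration of the study 24 months", and the title page gives February 2024 as the start.
- **Sizing.** Section 3.1: "the serum albumin level of the study subjects was the primary endpoint outcome indicator observed". No event count or power is given for RFS.

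**The concern.** The purpose and the schedule use different time scales. Section 1 describes prognosis after resection by 5-year survival (69.0% to 86.2%). By that yardstick, 6 months is early follow-up. Data that stop there hold no information on later recurrence, whatever the sample size.

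The lack of a cut-off date adds a second difficulty. Recurrence and survival are on the data form, so some later recurrences may be recorded and others not. The study is open and patients choose their group, so uneven capture could differ between groups and enter the Kaplan-Meier curves.

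At stake is what may be concluded about prognosis. Neither a null log-rank test nor an early difference would bear on the long-term part of the purpose.

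**Working it through.** **1. The plan's own figure.** The only sizing is for albumin: 34.2 (SD 3.9) against 37.5 (SD 5.4) g/L, two-sided 5%, 90% power. The difference is 3.3 and the pooled SD is √((3.9² + 5.4²)/2) = 4.71. A noncentral t calculation gives 44 per group (power 0.901), which matches the stated 88. The enrolment figure follows as 44 × 1.2 = 52.8, rounded to 53 per group, or 106. The sample size was therefore not chosen with RFS in mind.

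**2. Calendar.** Recruitment takes months 1 to 12. The last 6-month visit falls at about month 18 to 19, which leaves about 5 to 6 of the 24 months. Following everyone to month 24 would give about 24 months for the first patient and about 12 for the last.

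**3. Expected events.** The documents give no recurrence rate. Assumptions: proportion p recurring by 6 months of 10% or 20%, constant hazard, uniform accrual over 12 months, 106 patients.
- Hazard h = −ln(1 − p)/6 per month: 0.0176 for p = 10%, 0.0372 for p = 20%.
- Event fraction with follow-up uniform on 12 to 24 months = 1 − (e^(−12h) − e^(−24h))/(12h).
- p = 10%: 1 − (0.8100 − 0.6561)/0.2107 = 27.0%.
- p = 20%: 1 − (0.6400 − 0.4096)/0.4463 = 48.4%.
- Hazard ratio (HR) detectable with 80% power, two-sided 5%, 1:1 = exp(−2(1.96 + 0.84)/√events).
- For the dropout rows, 106 × 0.8 = 84.8 patients contribute.

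| Follow-up | Events, p = 10% | HR | Events, p = 20% | HR |
|---|---|---|---|---|
| 6 months, no loss | 10.6 | 0.18 | 21.2 | 0.30 |
| 6 months, 20% contribute nothing | 8.5 | 0.15 | 17.0 | 0.26 |
| To month 24, no loss | 28.6 | 0.35 | 51.3 | 0.46 |
| To month 24, 20% contribute nothing | 22.9 | 0.31 | 41.0 | 0.42 |

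Extending follow-up gives 2.4 to 2.7 times as many events.

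**4. Second set of assumptions.** Control-group recurrence of 10% to 40% at 12 months, 106 patients, no loss:

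| True HR | Events by 6 months (power) | Events to month 24 (power) | Events for 80% power |
|---|---|---|---|
| 0.5 | 4 to 18 (10% to 32%) | 12 to 45 (22% to 64%) | 66 |
| 0.7 | 5 to 21 (6% to 13%) | 13 to 50 (10% to 24%) | 247 |

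Both sets agree: longer follow-up adds information, but the study stays too small for a confirmatory RFS comparison.

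**The case against.** **Censoring at 6 months is not written.** A reader might infer that every recurrence-free patient will be censored at about 6 months. The documents do not say so. Section 7.2(3) sets no horizon, and the data form in 3.2 lists recurrence and survival without one. Figures are missing from the text available here, and section 5.2 has no readable content. This stands. What can be said is that no follow-up after 6 months is scheduled in the readable text and no cut-off is given.

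**RFS is secondary.** Albumin is the primary endpoint and drives the sample size. The test hypothesis in 2.3 names albumin, prealbumin and metabolic patterns, not recurrence. This also stands. A reader might infer that the study fails its main aim, and the documents do not support that.

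**Extension does not deliver long-term evidence.** Follow-up of 12 to 24 months is still far from 5 years. Power stays low, and an unadjusted log-rank test between groups chosen by patient wish limits any prognostic conclusion. This is correct. It governs how the extended result may be described, but does not remove the mismatch between purpose and schedule.

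**The spare months may be needed.** The documents do not say what the time after the last visit is for. A cut-off at month 24 itself leaves none for final data work within the stated duration. An earlier cut-off would give fewer events than the month-24 rows above.

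**Later detection would be uneven.** The protocol sets no recurrence surveillance schedule, so a record check or call finds only what routine care has found. This remains a limitation of the fix.

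**Conclusion.** The mismatch is real but limited in reach. Scheduled follow-up to 6 months supports a statement on early recurrence and none on long-term prognosis, and the missing cut-off leaves the RFS analysis undefined after that point. Under the first set of assumptions, about 11-21 events are expected by 6 months with no loss. Follow-up to month 24 would give about 29-51, or about 23-41 with 20% contributing nothing. These counts rest on assumed recurrence rates and a constant hazard; the statement about the time horizon does not.

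A reader might also infer that using the full 24 months would make RFS a sound long-term endpoint. It would not: 80% power would still need an HR of about 0.31-0.46, and follow-up would be medium-term. The point is a worthwhile correction at small cost to a secondary endpoint and to the wording of the purpose.

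**What to change.** In sections 6.5 and 7.2(3):
- Keep the 1, 3 and 6-month visits as they are.
- Add collection of recurrence (with date of detection) and survival status for every patient in both groups, by record check or telephone, to one common cut-off date within the 24-month study.
- Name that date as the censoring date for the Kaplan-Meier and log-rank analyses.
- Label the analysis exploratory and call it medium-term (about 12 to 24 months).
- State that the follow-up period in section 4.4, item 6 remains the 6-month intake follow-up, so that a longer recurrence follow-up does not widen the adherence-based removals.

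The cost is at most 106 status checks and a wording change, with no extra patients, clinic visits or blood draws. The RFS result would come up to about 5 to 6 months later than the 6-month laboratory data, and detection would depend on routine surveillance.

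If this is not done, replace long-term prognosis in the synopsis and section 2.1 with recurrence within 6 months, and state that no long-term conclusion will be drawn. That costs only a narrower claim.
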